2. OBJECTIVES

2.1. Primary Objective

- Evaluate the long-term safety of multiple doses of ALN-GO1 in patients with PH1

2.2. Secondary Objectives

- Evaluate the PD effect of ALN-GO1 on urinary oxalate excretion
- Characterize the effect of ALN-GO1 on markers of renal function

2.3. Exploratory Objectives

- Characterize the pharmacokinetics (PK) of ALN-GO1
- Evaluate the PD effect of ALN-GO1 on urinary glycolate excretion, plasma oxalate concentration, plasma glycolate concentration, and urine oxalate:creatinine ratio
- Evaluate the incidence of anti-drug antibodies (ADA)

3. ENDPOINTS

3.1. Primary Endpoint

- Incidence of adverse events (AEs)

3.2. Secondary Endpoints

- Change in 24-hour urinary oxalate corrected for body surface area (BSA) over time
- Change in 24-hour urinary oxalate:creatinine ratio over time
- Change in estimated glomerular filtration rate (eGFR) over time

3.3. Exploratory Endpoints

- Describe the effects of ALN-GO1 on other safety parameters, including assessments of vital signs, electrocardiograms (ECG), renal ultrasounds, clinical laboratory parameters, and physical examinations.
- Assess ALN-GO1 plasma PK parameters including maximum plasma concentration (C_{max}), time to maximum plasma concentration (t_{max}), elimination half-life ($t_{1/2\beta}$), area under the concentration-time curve (AUC), fraction of drug excreted in urine (Fe), apparent clearance (CL/F), and apparent volume of distribution (V/F).
- Change from Baseline over the course of the study in the following PD parameters:
 - Urinary glycolate excretion
 - Plasma oxalate concentration
 - Plasma glycolate concentration

- Spot urinary oxalate:creatinine ratio
- Incidence of ADA

4. INVESTIGATIONAL PLAN

4.1. Summary of Study Design

This is a multicenter, open-label extension study to evaluate the long-term safety, PK, and PD of subcutaneously administered ALN-GO1 in patients with PH1 who completed Study ALN-GO1-001.

Consented eligible patients will enroll in this study and initially receive subcutaneous (SC) injections of ALN-GO1 at the same dose and regimen as they received in Study ALN-GO1-001. Based on emerging data, the SRC may authorize an alteration of dose and/or dose regimen to one that is no higher than the highest dose evaluated in either Part A or Part B of Study ALN-GO1-001. If such an authorization occurs, dose and/or dose regimen alteration may occur for an individual patient or entire cohort. This alteration may apply to subsequent doses for patients already enrolled and previously dosed in the study and/or to the initial dose and regimen for patients who have not yet been dosed in this study. Patients will be assessed for safety at each study visit.

PD assessments will be completed quarterly over the first 12 months on study, and approximately every 6 months thereafter for the study duration. PK assessments will be conducted during the first 12 months on study ([Table 1](#)).

Patients may receive ALN-GO1 as long as they do not fulfill any of the study discontinuation criteria (see [Section 5.3.1](#)) or until ALN-GO1 is commercially available in the patient's territory or the ALN-GO1 development program is discontinued (whichever comes first).

4.2. Duration of Treatment

The estimated duration of treatment in this study is up to 54 months.

4.2.1. Definition of the End of Study for an Individual Patient

The End of Treatment (EOT) visit is defined as the visit when the final dose of ALN-GO1 is administered. The End of Study (EOS) visit is defined as the visit 3 months after the EOT. Patients are considered to have completed the study when they have completed the EOS visit.

Patients who discontinue treatment but remain on study for assessments are considered to have reached the end of the study upon completing 6 months of monitoring following the final dose of ALN-GO1.

For patients who withdraw from the study, see [Section 5.3.2](#).

4.3. Number of Patients

Up to 20 patients are planned for enrollment in this study.

4.4. Method of Assigning Patients to Treatment Groups

Not applicable. This is an open-label study.

4.5. Blinding

Not applicable. This is an open-label study.

4.6. Safety Review Committee

An SRC will perform ongoing reviews of safety, tolerability, and available study data collected in this study with the primary purpose of protecting the safety of patients. At a minimum, reviews will be conducted every 3 months.

The SRC will be comprised of the Sponsor Medical Monitor, a Medical Monitor from the contract research organization (CRO), 3 Investigators from participating clinical study centers or their designees, and an independent pediatrician experienced in clinical investigation who is not a study investigator.

The SRC is governed by a charter that was signed prior to enrollment of the first subject.

5. SELECTION AND WITHDRAWAL OF PATIENTS

5.1. Inclusion Criteria

Each patient must meet all of the following inclusion criteria to be eligible for enrollment in the study:

1. Enrollment within 12 months of completion of Study ALN-GO1-001 and in the opinion of the investigator, tolerated the study drug
2. If taking vitamin B6 (pyridoxine), willing to remain on a stable regimen for the study duration
3. Women of child-bearing potential must have a negative pregnancy test, cannot be breast feeding, and must be willing to use a highly effective method of contraception from 14 days before first dose and throughout study participation until the completion of the follow-up period
4. Willing and able to comply with the study requirements and to provide written informed consent and assent in the case of patients under the age of legal consent, per local and national requirements

5.2. Exclusion Criteria

Each patient must not meet any of the following exclusion criteria to be eligible for enrollment in the study:

1. Any uncontrolled or serious disease, or any medical or surgical condition (with the exception of PH1) that may either interfere with participation in the clinical study, and/or put the patient significant risk (according to the Investigator's judgment) if he/she participates in the clinical study

2. An underlying known disease or surgical or medical condition (with the exception of PH1) that in the opinion of the investigator might interfere with the interpretation of the clinical study results
3. Requirement for chronic dialysis
4. Triplicate 12-lead ECG with clinically significant abnormalities at Baseline visit, at the discretion of the investigator
5. Echo assessment of abnormal left ventricular systolic function, defined as left ventricular ejection fraction <55% at Screening
6. Abnormal for aspartate aminotransferase (AST)/alanine aminotransferase (ALT) and any other clinical safety laboratory result considered clinically significant and unacceptable by the Investigator at Baseline, at discretion of investigator
7. Legal incapacity or limited legal capacity at Screening of patient, parent, or legal guardian

5.3. Removal from Therapy or Assessment

Patients or their legal guardian (in case patient has not reached the age of majority) are free to discontinue treatment or withdraw from the study at any time and for any reason, without penalty to their continuing medical care. Any discontinuation of treatment or withdrawal from the study must be fully documented in the electronic case report form (eCRF), and should be followed up by the Investigator. The Investigator may withdraw a patient at any time if this is considered to be in the patient's best interest.

Discontinuation of study drug and withdrawal from the study are described in Section [5.3.1](#) and Section [5.3.2](#), respectively.

5.3.1. Discontinuation of Study Drug

The Investigator or designee may discontinue dosing in a patient if the patient:

- Is in violation of the protocol
- Experiences a serious or intolerable AE
- Becomes pregnant
- Is found to be considerably noncompliant with the protocol requirements

The Investigator will confer with the Sponsor or Medical Monitor before discontinuing dosing in the patient. Patients who are pregnant will be discontinued from dosing immediately (see Section [7.4.8.6](#) for reporting and follow-up of pregnancy). In general, patients who discontinue study drug dosing for any reason will be encouraged to complete the End of Treatment assessments and safety and PD follow up visits so that their experience is captured in the final analyses. Patients who discontinue study drug but who remain on study may receive local standard of care treatment for their disease, as applicable.

5.3.2. Withdrawal From Study

A patient/legal guardian may withdraw from the study at any time. If a patient/legal guardian chooses to withdraw from the study, every effort should be made to conduct the End of Treatment assessments and safety and PD follow-up visits (see [Table 1](#)).

When a patient withdraws from the study, the primary reason for discontinuation must be recorded in the appropriate section of the electronic case report form (eCRF) and all efforts will be made to complete and report the observations as thoroughly as possible. If a patient withdraws due to a serious adverse event (SAE), the SAE should be followed as described in Section [7.4.8](#). There will be no replacements of patients who withdraw from this study.

6. TREATMENTS

6.1. Treatments Administered

Study drug supplied for this study must not be used for any purpose other than the present study and must not be administered to any person not enrolled in the study. Study drug that has been dispensed to a patient and returned unused must not be re-dispensed to a different patient.

6.2. Investigational Study Drug

Detailed information describing the preparation, administration, and storage of ALN-GO1 is provided in the Pharmacy Manual.

6.2.1. Description

ALN-GO1 is a synthetic, double-stranded small interfering RNA oligonucleotide directed against *HAO1* mRNA that is covalently linked to a ligand containing 3 *N*-acetylgalactosamine residues.

6.2.2. Dose and Administration

Initially, patients will receive SC injections of ALN-GO1 at the same dose and regimen as they received in Study ALN-GO1-001. Based on emerging data, the SRC may authorize an alteration of dose and/or dose regimen to one that is no higher than the highest dose evaluated in either Part A or Part B of Study ALN-GO1-001. If such an authorization occurs, dose and/or dose regimen alteration may occur for an individual patient or entire cohort. This alteration may apply to subsequent doses for patients already enrolled and previously dosed in the study and/or to the initial dose and regimen for patients who have not yet been dosed in this study.

Patients will be administered study drug by SC injection(s). The body weight obtained within 4 months before the study visit day or dosing day will be used for calculation of the ALN-GO1 dose to be administered.

Study drug will be administered under the supervision of the Investigator or designee. Detailed instructions for study drug administration are found in the Pharmacy Manual.

Dosing will be permitted at a location other than the study center (for example, the patient's home) by a healthcare professional with the oversight of the Investigator at all time points,

provided the patient has tolerated ALN-GO1 administered in the clinic. However, continued study drug administration at the study center should be considered for patients who have ongoing study drug-related AEs, worsening injection site reactions with repeat dosing, or for anyone in the opinion of the Investigator who would benefit from clinical observation following dosing.

If the patient is unable to come to the study site, and a visit by a healthcare professional is not possible due to circumstances related to the COVID-19 pandemic, ALN-GO1 may be administered by the patient or the caregiver under the oversight of the Investigator, and following consultation with the Medical Monitor, as allowed by applicable country and local regulations. In such cases, the patient or caregiver must receive appropriate training on ALN-GO1 administration prior to dosing. This measure is intended to remain in effect only during periods of time when the COVID-19 pandemic impedes the ability of patients to travel to the study site and healthcare professionals to go to patients' homes for dosing.

The sites of injection may be the abdomen, the upper arms, or thighs. If a local reaction around the injection site occurs, photographs may be obtained.

Patients whose disease progresses to requiring a dialysis regimen will continue on their planned dosing regimen. The ALN-GO1 dose will be administered as soon as feasible following the end of dialysis, eg, within 2 hours of completing the dialysis session. If a patient does not receive a dose of ALN-GO1 within the specified dosing window, the Investigator should contact the Medical Monitor. After such consultation, the dose may be administered or considered missed and not administered.

If a patient misses multiple doses of study drug, the Investigator, in consultation with the Medical Monitor, will discuss whether the patient will be able to continue on the study.

Additional details can be found in the Pharmacy Manual. In addition, instructions and procedures related to administration of ALN-GO1 by a patient or caregiver will be provided in the Patient/Caregiver Storage and Administration Instructions.

6.2.3. Dose Modifications

Dose modification is not permitted in this study, except as noted in Section [6.2.2](#).

If a study drug-related AE occurs in a patient that the Investigator judges as presenting a potential risk to the patient for further dosing, the study drug dose may be held at the discretion of the Investigator and the Medical Monitor should be contacted.

6.2.3.1. Liver Function Test Criteria for Withholding, Monitoring and Stopping Study Drug Dosing

1. LFT results from the previous visit should be reviewed prior to dosing.
2. For any ALT or AST elevation $>3\times$ ULN central laboratory results should be used to guide subsequent monitoring as detailed in [Table 2](#).
3. For any ALT or AST elevation $>3\times$ ULN:
 - a. If local laboratory results are obtained, confirm using central laboratory, as soon as possible, ideally within 2 to 3 days, but no later than 7 days.
 - b. If an alternative cause is found, provide appropriate care.

- c. If an alternative cause is not found, perform assessments per [Table 2](#) and [Table 4](#).
4. For any ALT or AST elevation $>3\times$ ULN without alternative cause that is accompanied by clinical symptoms consistent with liver injury (eg, nausea, right upper quadrant abdominal pain, jaundice) or elevated bilirubin to $\geq 2\times$ ULN or INR ≥ 1.5 , permanently discontinue dosing.
5. For confirmed ALT or AST elevations $>3\times$ ULN without alternative cause and not accompanied by symptoms or elevated bilirubin $\geq 2\times$ ULN or INR ≥ 1.5 , see [Table 2](#) (below):

Table 2: Monitoring and Dosing Rules for Asymptomatic Patients with Confirmed Isolated Elevations of ALT and/or AST $>3\times$ ULN, with No Alternative Cause Identified

Transaminase Level	Action
$>3\times$ to $5\times$ ULN	
• May continue dosing• Evaluate the initial elevation in LFT per the following assessments:
• Table 4 (all assessments to be performed once)• Hematology, serum chemistry and LFT per Table 3• Coagulation (prothrombin time, partial thromboplastin time, international normalized ratio)• Monitor LFTs at least every two weeks• If elevation persists for ≥ 2 months, must discuss with the medical monitor before continuing dosing
$>5\times$ to $8\times$ ULN	
• Hold study drug dosing until recovery to $\leq 1.5\times$ ULN or baseline; may resume dosing after discussion with the Medical Monitor• Evaluate the initial elevation in LFT per the following assessments
• Table 4 (all assessments to be performed once)• Hematology, serum chemistry and LFT per Table 3• Coagulation (prothrombin time, partial thromboplastin time, international normalized ratio)• Monitor LFTs at least weekly until ALT and/or AST is declining on 2 consecutive draws, then may decrease monitoring to biweekly• If ALT or AST rises to $>5\times$ ULN following resumption of dosing, permanently discontinue dosing
$>8\times$ ULN	Permanently discontinue dosing after confirmation of the transaminase value at the central laboratory.

Abbreviations: ALT=alanine transaminase; AST=aspartate transaminase; LFT=liver function test(s); ULN=upper limit of normal.

Notes: In addition to these criteria, other assessments or evaluations may be performed per Investigator discretion, as appropriate.

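### Protocol Table 2, >3× to 5× ULN row: dosing may continue, but INR, a permanent-stop criterion, is required only at the first work-up and not at the two-weekly repeats

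*Protocol*

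**What the plan says.** Protocol 6.2.3.1 builds its liver rules in steps.

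- **Item 1 (before each dose):** "LFT results from the previous visit should be reviewed prior to dosing".
- **Item 4 (permanent stop):** an unexplained ALT or AST above 3× ULN "that is accompanied by clinical symptoms consistent with liver injury", or with bilirubin ≥2× ULN, or with INR ≥1.5.
- **Item 5 (entry to Table 2):** confirmed elevations "without alternative cause and not accompanied by symptoms or elevated bilirubin" at the 2× ULN level, and without INR ≥1.5.
- **Table 2, >3× to 5× ULN:** dosing is allowed to go on. A work-up list stands under "Evaluate the initial elevation in LFT per the following assessments". It contains the Table 4 panel, the Table 3 hematology, chemistry and LFTs, and a coagulation line naming prothrombin time, partial thromboplastin time and INR. The follow-up instruction is separate: "Monitor LFTs at least every two weeks". Then: "If elevation persists for ≥ 2 months, must discuss with the medical monitor before continuing dosing".
- **Table 2, >5× to 8× ULN:** "Hold study drug dosing until recovery to" 1.5× ULN or below, or baseline. Above 8× ULN, dosing ends.
- **Table 2 note:** "other assessments or evaluations may be performed per Investigator discretion, as appropriate".

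Table 3 lists liver function tests as AST, ALT, ALP and total and direct bilirubin, and has no coagulation panel. Table 4 has no INR. Section 7.4.7.3 mentions coagulation after an LFT abnormality, but places it beside assessments left to the Investigator's discretion and gives no repeat schedule. SAP 7.3.1 lists coagulation among the parameters to summarise, which does not oblige anyone to collect it.

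**The concern.** A stop rule works only if its inputs are measured while the patient is exposed. Item 4 applies for as long as the unexplained elevation stays above 3× ULN, and the absence of all three triggers is what allows management under Table 2. In the one row where dosing continues, bilirubin is re-measured at every repeat and symptoms can be asked about at any contact. INR is not re-measured unless someone chooses to order it.

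The patient at risk has a normal INR at the first work-up and later reaches 1.5 or more while bilirubin stays below 2× ULN and no symptoms appear. With exact adherence to the protocol, that patient meets a permanent-stop criterion, goes on being dosed, and has no required test that would reveal it.

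**Working it through.** The plan gives no figure to reproduce. The check compares the stop rule with the tests required, then counts draws and doses.

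**1. Inputs to item 4 against required tests, >3× to 5× ULN row**

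| Item 4 input | First work-up | Two-weekly repeat | Pre-dose review (item 1) |
|---|---|---|---|
| ALT/AST | required | required | covered |
| Bilirubin | required | required | covered |
| Symptoms | clinical | can be asked about | can be asked about |
| INR | required (coagulation line) | not required | not covered |

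INR is the only laboratory input with no required repeat. Reading LFTs to include INR is not supported: Table 3 omits it, and both Table 2 and SAP 7.3.1 name coagulation separately from LFTs.

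**2. Repeat draws before the mandatory discussion.** Inputs: 2 months, taken as 56 days on the protocol's 28-day schedule, and draws at least every 14 days. 56 / 14 = 4 draws (days 14, 28, 42 and 56, with detection as day 0). Required INRs now: 1 (initial). With the fix: 1 + 4 = 5.

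**3. Doses due in the window.** The regimens are in SAP 2.1. The count runs over every possible alignment of the dosing cycle with day 0.

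- Monthly (28 days): days 1–56 hold 56 / 28 = 2 doses for every alignment. Counting days 0–56, there are 3 when a dose falls on day 0 (1 of 28 alignments) and 2 otherwise.
- 3-monthly (84 days): at least one dose for 56 / 84 = 66.7% of alignments (days 1–56) or 57 / 84 = 67.9% (days 0–56); otherwise none.

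These are all the doses in the window, so they are ceilings. The doses that matter are those given after INR crosses 1.5, and the documents do not allow that time to be estimated.

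**4. Safety Review Committee (Protocol 4.6).** At its minimum frequency, taken as every 84 days, a review falls in days 1–56 for 56 / 84 = 66.7% of alignments. It cannot review an INR that was not drawn.

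**5. Blood cost of the fix.** Tube volume and the lowest patient weight are not in the documents. Assumption: 1 to 3 mL per tube. Table 6 lower limits at 16 kg: 32 mL per 24 hours and 64 mL per 30 days.

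- One tube: 1/32 = 3.1% to 3/32 = 9.4% of the 24-hour limit.
- Two added tubes in the first 30 days (days 14 and 28; coagulation at day 0 is already required): 2/64 = 3.1% to 6/64 = 9.4% of the 30-day limit.
- Three tubes in a later 30-day span (days 14, 28 and 42): 3/64 = 4.7% to 9/64 = 14.1%.
- Three tubes at 10 kg (40 mL per 30 days): 7.5% to 22.5%. At 36 kg (144 mL): 2.1% to 6.2%.

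**The case against.** The strongest reply is that this is a choice of monitoring intensity and not a contradiction. The plan takes an INR at the outset, repeats transaminases and bilirubin at least every two weeks, and stops on symptoms or bilirubin. Amendment 2 reworked this coagulation line, with reduced blood sampling among its aims. The choice can stand as deliberate, but it still leaves a mandatory stop criterion resting on an optional test.

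The text is also less closed than it first looks. Items 3 and 4 speak of any elevation above 3× ULN, the restriction to a single performance is attached to Table 4 and not to coagulation, and Section 7.4.7.3 could be read as calling for coagulation after a new LFT abnormality. An Investigator applying item 5 afresh to a repeat value would have reason to check INR. Even so, Table 2 ties coagulation to the initial elevation, and a rise in INR without a new LFT abnormality triggers nothing.

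Other safeguards exist. The Table 2 note and Section 7.4.7 allow extra tests. ALT or AST above 3× ULN is an adverse event of clinical interest (7.4.8.1). The Investigator may hold a dose for a drug-related event judged to be a risk (6.2.3). None of these requires an INR. The 7.4.7 instruction to repeat a clinically relevant abnormal test helps when the first INR is already abnormal, not when it starts normal.

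Two points stand. The dose counts describe the exposure window and not harm. And two-weekly INR is more than dosing decisions strictly need on the 3-monthly regimen; a current INR before each dose would be lighter on children.

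**Conclusion.** The concern holds. In the >3× to 5× ULN row the protocol permits dosing while one of its own permanent-stop criteria goes unmeasured by any requirement after the first work-up. Up to the mandatory discussion that means 4 draws without a required INR, and at most 2 or 3 doses on a monthly regimen or 0 or 1 on the 3-monthly regimen. The discussion itself does not call for an INR, so the gap can continue afterwards.

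The gap is confined to this row, because dosing is held at >5× to 8× ULN and stopped above that. The number of patients affected is probably small and cannot be estimated, given at most 20 planned and no stated frequency of such elevations. The counts rest on 28-day months and draws at the minimum frequency. This should be changed because the remedy is cheap, not because harm is likely.

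**What to change.** **Protocol Table 2, >3× to 5× ULN row:** require LFTs and INR at least every two weeks for as long as unexplained ALT or AST stays above 3× ULN and dosing continues.

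**Protocol 7.4.7.3:** reword so that coagulation is plainly required, in line with Table 2, and only the other assessments are discretionary.

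The stopping thresholds stay as they are and the SAP needs no change. If paediatric blood volume is the deciding constraint, a current INR before each dose is a lighter variant, though it would not put INR on the same schedule as bilirubin.

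The cost is a wording amendment and one coagulation tube at draws already required, in the few patients in this row. The downside is extra blood from children, in a protocol that has cut assessments to spare them (Section 1.5). Other samples draw on the same Table 6 allowance, so the total has to be checked patient by patient.
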